
	
All remaining Group 2 subjects will enter Cohort 3 in ARC004 EM and will be randomized in a 1:1:1 ratio to ongoing treatment with AR101.
 
• Cohort 3A: QD for 56 weeks• Cohort 3B: QD for 28 weeks followed by QOD for 4 weeks and then BIW for 24 weeks, as tolerated• Cohort 3C: QD for 28 weeks followed by QOD for 4 weeks and BIW for 24 weeks, and finally QW for 28 weeks, as tolerated. 
At the end of each treatment period, qualifying subjects will undergo a maximum 4043 mg cumulative Exit DBPCFC and complete participation in ARC004.
 
The Exit Visit will complete subject participation in ARC004 with one exception: If a study site has not yet received approval for ARC008, subjects will receive additional AR101 and will continue dosing and visits in ARC004 until ARC008 is able to accept these subjects at the study site. Subjects will return to the study site for an unscheduled visit every 14 weeks to receive AR101 sachets for dosing at home and to ensure subject safety.
 
Throughout ARC004 EM, the first 2 doses at extended dosing intervals (BIW, QW, and QOW) will be administered under direct supervision in the clinic; QOD doses may be initiated at home. Thereafter, the doses will be administered at home as tolerated, and recorded in the subject diary. Investigators may, at their discretion, bring subjects back to the research unit for an observed dose at any time. All AR101 doses will be judged by the investigator to be tolerated or not tolerated according to criteria previously established in ARC003 and specified in Section 6.5.2.
 
Any subject receiving nondaily dosing (QOD, BIW, QW, or QOW) who has 1 related SAE; 1 related AE graded severe; 2 related AEs occurring on separate occasions, both graded moderate; or 3 consecutive doses judged “not tolerated” will be considered a treatment failure in the statistical analysis of each cohort and discontinued from ARC004 for safety reasons. Such subjects may be eligible to enroll in ARC008 on a QD regimen. If a site has not yet received approval for enrollment of subjects into ARC008, the subject will begin daily dosing and have visits in the Repeat Up-dosing period in ARC004. Once the subject reaches the target dose of 300 mg daily and maintains this dose for 2 weeks, that subject will be able to continue this dosing regimen and enroll in ARC008 when available.
 
Early discontinuations due to related AEs, and subjects unable to tolerate a prespecified amount (either ≥ 443 mg or ≥ 1043 mg of cumulative) peanut protein during the Exit DBPCFC, will be considered failures. If failures affect greater than 50% of any cohort, then prolongation of the dosing interval in any subsequent cohort will cease, and the remaining subjects will be administered AR101 300 mg at the longest dosing interval tolerated by a previous cohort (Section 7.8.3).
 
Early Discontinuations:
 
Subjects who are discontinued for an AE will have that AE evaluated from the onset until the event is resolved or medically stable, or for 30 days after the Early Discontinuation Visit, whichever comes first.
 
Subjects who are discontinued for reasons other than an AE and who do not enter ARC008 will be followed for safety for 30 days after the last dose of AR101, 2 weeks after the last food challenge, or until resolution or stabilization of all AEs ongoing at the time dosing is stopped, whichever is longer.
 
In addition, subjects who are discontinued from further AR101 dosing due to chronic or recurrent gastrointestinal (GI) AEs will be followed monthly for a minimum of 6 months, or until resolution or stabilization of all GI AEs.
 
For subjects who do not tolerate their nondaily dosing regimen and subjects who switch to daily dosing after missing their nondaily dose for > 3 days, the exit

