^a All mg doses shown refer to milligrams of peanut protein.

DBPCFC Schedule (Post-Maintenance: Group 1 only; Post-Extended Maintenance: Groups 1 and 2)	
Challenge Dose, mg	Cumulative Dose, mg
3	3
10	13
30	43
100	143
300	443
600	1043
1000	2043
2000	4043

Figure 1: Study Schematic

Diamonds represent DBPCFCs; all challenges in ARC004 will be to a total of 4043 mg cumulative peanut protein, according to the table above.

The initial ARC004 DBPCFC for Group 1 will be completed after approximately 24-week maintenance period

QD = daily, QOD = every other day, BIW = twice weekly, QW = once weekly, QOW = every other week

NOTE: The BIW interval begins with 4 weeks of QOD dosing before transitioning to 24 weeks of BIW dosing, as tolerated

Group 1: Total duration varies, ranging from approximately 88 to 136 weeks

Group 2, Cohort 1: 28 weeks

Group 2, Cohort 2: 28 weeks

Group 2, Cohort 3A: 56 weeks

Group 2, Cohort 3B: 56 weeks

Group 2, Cohort 3C: 84 weeks

TABLE OF CONTENTS

LIST OF ABBREVIATIONS	19
1 BACKGROUND AND RATIONALE	21
1.1 Background	21
1.2 Clinical Trials of AR101	22
1.2.1 ARC001	22
1.2.2 ARC002	23
1.2.3 ARC003	23
1.3 Rationale for the Current Study	24
1.4 Known and Potential Risks and Benefits of AR101.....	25
1.4.1 Risks	25
1.4.2 Benefits.....	26
2 OBJECTIVES.....	26
2.1 Primary Objective	26
2.2 Secondary Objectives.....	27
3 STUDY DESIGN	27
3.1 Study Periods	29
3.1.1 Initial Escalation (Group 1 Only)	30
3.1.2 Up-dosing (Group 1 Only).....	30
3.1.3 Repeat Up-dosing (Subjects Switching to Daily Dosing).....	31
3.1.4 Maintenance.....	32
3.1.5 Extended Maintenance.....	33
4 SELECTION AND WITHDRAWAL OF SUBJECTS	35
4.1 Inclusion Criteria.....	35
4.2 Exclusion Criteria.....	35
4.3 Early Termination	36
4.3.1 Criteria for Early Termination	36
4.3.2 Follow-up of Subjects.....	37
4.3.3 Subject Replacement	37
5 STUDY TREATMENT	37
5.1 Formulation, Packaging, and Labeling.....	37
5.2 Preparation, Administration, and Dosage.....	38
5.3 Drug Accountability.....	39
5.4 Assessment of Compliance with Study Treatment and Monitoring	40
5.5 Modification of Study Treatment	40
5.6 Concomitant Medications	40
5.7 Prophylactic Medications	40
5.8 Rescue Medications	40
5.9 Symptomatic Treatment for Chronic and/or Recurrent Adverse Events.....	41
5.10 Prohibited Medications	41
6 STUDY PROCEDURES	42
6.1 Enrollment and Randomization.....	42
6.2 Screening and Baseline Visit – (Group 1 and Group 2).....	42
6.3 Study Visits	44
6.3.1 Initial Escalation: Day 1 (Group 1).....	44

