3.1.5 Extended Maintenance

The EM periods will differ between and within the 2 groups in duration and dosing regimen (see below and [Figure 1](#)). However, all EM subjects who complete their dosing regimen, regardless of group or cohort assignment, will have an Exit DBPCFC up to a single highest dose of 2000 mg of peanut protein (4043 mg cumulative).

Group 1

All Group 1 subjects who tolerate ≥ 443 mg cumulative peanut protein in the Post-Maintenance DBPCFC will enter the EM period. Subjects who do not tolerate ≥ 443 mg are not eligible to continue for safety reasons. The EM period for Group 1 subjects will initially consist of QD dosing while the Group 2 cohorts are undergoing evaluation as outlined below. Conditional upon the safety and DBPCFC outcomes assessed in the Group 2 participants, Group 1 subjects may have their dosing interval serially lengthened from QD to QOD, QOD to BIW, BIW to QW, and QW to QOW, as tolerated. The duration of each of these interval extension periods will be adjusted, based on Group 2's experience, from between 8 to 28 weeks, as tolerated. In clinic visits during the EM for Group 1 subjects will continue to occur every 14 weeks. Following the completion of the longest tested dosing interval, Group 1 subjects will then undergo an Exit DBPCFC and ARC004 will conclude.

Group 2

As they enter ARC004, Group 2 subjects will be consecutively assigned to 1 of 3 cohorts and continue to receive AR101 in the following fashion:

- The first 120 Group 2 subjects (ie, 1 to 120) entering ARC004 will form Cohort 1 and continue to receive QD treatment for 28 weeks as tolerated and then undergo an Exit DBPCFC.

- The next 50 Group 2 subjects (ie, 121 to 170) entering ARC004 will form Cohort 2, receiving AR101 300 mg QOD for 4 weeks, and then BIW for 24 weeks, as tolerated, and then undergoing an Exit DBPCFC.
- All remaining Group 2 subjects (ie, 171 to end) entering ARC004 will form Cohort 3. Upon entering Cohort 3, these subjects will be randomized 1:1:1 to receive AR101 in 28 week periods, as follows. Cohort 3A will receive 300 mg QD for 56 weeks as tolerated and then undergo an Exit DBPCFC. Cohort 3B will receive 300 mg QD for 28 weeks and then 300 mg QOD for 4 weeks followed by BIW for 24 weeks, as tolerated, and then undergo an Exit DBPCFC. Cohort 3C will receive 300 mg QD for 28 weeks, 300 mg QOD for 4 weeks followed by BIW for 24 weeks, and then 300 mg QW for 28 weeks, as tolerated, and then undergo an Exit DBPCFC.

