6.3.8 All Subjects (Groups 1 and 2): Extended Maintenance Visits

The EM period begins upon entry in ARC004 for Group 2, and following completion of the Post-Maintenance DBPCFC for Group 1.

6.3.8.1 Alternate Dosing Initiation Visit: Day 1

Subjects in Cohorts 2, 3B, and 3C will change to BIW dosing once they have tolerated QOD dosing for 4 weeks. Subsequently Cohort 3C may extend the interval further. Subjects extending their dosing interval (eg, QOD to BIW, BIW to QW, QW, to QOW) will do so by taking the first 2 doses of the new interval under observation in clinic (except QOD). Every effort should be made to ensure the new interval is the appropriate interval. Some or all of the following procedures may be performed at the first of these 2 visits, according to the procedures outlined in the Schedule of Events:

- Diet (food allergen) history.
- Concomitant medication update.
- Symptom-directed physical examination.
- Pre-dose vital sign measurement (BP, PR, body temperature).
- Peak expiratory flow rate (PEFR), performed in all subjects 6 years of age or older, measured at approximately the same time for each assessment visit. Three attempts of PEFR should be performed, and the best attempt selected. For subjects 4 or 5 years of age: peak flow rates are to be attempted, but reliable performance is not required for the subject to enter the study or undergo study procedures at the investigating physician's discretion. The attempt must be documented, and a clinical assessment is required.
- Spirometry* (FEV₁), performed when PEFR shows a clinically relevant reduction or the subject shows clinical deterioration (e.g., active wheeze on physical examination); 3 attempts of FEV₁ should be performed, and the best attempt selected.

*Only for subjects 6 years of age and older who are able to adequately perform spirometry. In order to assess whether the subject is able to adequately perform spirometry, the spirometry must be attempted, and any attempt must be documented.

- Urine pregnancy test.
- Oral administration of AR101.
- Skin prick test.
- Post-dose vital sign measurements (BP, PR) within 15 to 30 minutes post dose, prior to discharge, and as indicated per investigator discretion during the post-dose observation period. Subjects with moderate or severe symptoms should be monitored every 30 minutes.
- Blood draw to collect samples for:

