Whenever this number is greater than 50%, then this stopping rule is met and further prolongation of the dosing interval in any subsequent cohort will cease. As an additional safety precaution, if individual stopping rules (eg, due to AEs) are invoked in 10 of the first 20 subjects to enroll in any cohort, further enrollment in that cohort will cease. Finally, the SMC retains the authority to stop further enrollment into a cohort at any time for any reason. If any of these conditions transpire, all remaining subjects, including those ongoing subjects in the terminated cohort, and future subjects, will be administered AR101 300 mg at the longest interval tolerated by a previous cohort.

*Assumptions = Up to approximately 500 ARC003 completers (having received active or placebo in ARC003 at a 3:1 ratio) are projected for recruitment into ARC004. This assumes a loss of 15% of the randomized ARC003 population due to attrition, AEs, etc. Thus, the planned sizes for the ARC004 cohorts is as follows, though the actual number may vary due to recruitment:

- Cohort 1 = 120, prespecified
- Cohort 2 = 50, prespecified
- Cohort 3 = 175, distributed equally across Cohorts 3A, 3B, 3C
- Group 1 = 130 (25% of ARC003 enrollment, accounting for 5% dropout)

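### The cohort stopping rule assigns remaining subjects to the longest tolerated interval instead of capping it, so read literally it could move Cohort 3A from QD to BIW

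*Protocol*

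**What the plan says.** Protocol 7.8.3 gives three conditions: a treatment failure rate above 50% of the planned cohort size; individual stopping rules invoked in 10 of the first 20 subjects enrolled in a cohort; and an SMC decision to stop enrollment into a cohort for any reason. For the first condition only, the text adds that "further prolongation of the dosing interval in any subsequent cohort will cease". All three then lead to one action. It covers "all remaining subjects, including those ongoing subjects in the terminated cohort, and future subjects". The end of that list and the instruction itself read: "and future subjects, will be administered AR101 300 mg at the longest interval tolerated by a previous cohort".

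The Protocol Synopsis (Study Procedures, Extended Maintenance) carries the same action for the 50% rule alone: "the remaining subjects will be administered AR101 300 mg at the longest dosing interval tolerated by a previous cohort".

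Cohort 3A's regimen is fixed in Protocol 3.1.5: "Cohort 3A will receive 300 mg QD for 56 weeks as tolerated and then undergo an Exit DBPCFC". Cohort 2, which enrolls earlier, takes QOD for 4 weeks and then BIW for 24 weeks.

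Protocol 3.1.5 and 7.8.3 also contain a general guard. It bars a longer interval when evidence from previous cohorts makes more frequent or more severe AEs, or lost desensitization, more likely than not.

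**The concern.** A stopping rule for interval lengthening should only hold intervals where they are or shorten them. The post-stop sentence instead states which interval remaining subjects will receive. For a subject already on a longer interval it works as intended. For a subject assigned to QD it points the wrong way once any previous cohort has tolerated something longer than QD.

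Two things are at stake. First, subjects who are stable on daily dosing would have their interval lengthened because another arm ran into trouble. Second, Cohort 3A is the only Cohort 3 arm randomized to QD throughout, and it shares the 56-week exit with Cohort 3B. Changing its regimen from the date of a stop would blur that comparison. Protocol section 9 makes comparisons between cohorts exploratory, so the second loss is to interpretation and not to a formal test. Data already collected in 3A, and subjects who have finished, would be unaffected.

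**Working it through.** The plan states no figure for this point, so the check is a reading of the text plus simple counts from the planned sizes.

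**Step 1. Who is covered.** Suppose Cohort 2 tolerated BIW and Cohort 3B or 3C then meets a condition. If each arm counts as a cohort, 3A falls under the remaining subjects. If Cohort 3 as a whole counts as the cohort, 3A falls under the ongoing subjects of the terminated cohort. It is covered either way, and the interval assigned is BIW.

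**Step 2. Whether other text prevents it.**
- The statement that prolongation will cease is attached to the 50% condition and to subsequent cohorts. The other two conditions end enrollment only, yet lead to the same assignment sentence.
- The guard depends on evidence of harm from previous cohorts. In this scenario the previous cohort tolerated BIW, and a parallel arm such as 3B is not clearly a previous cohort. The guard may block the move, but it does not have to.

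**Step 3. How many subjects.** Protocol 7.8.3 plans "Cohort 3 = 175, distributed equally across Cohorts 3A, 3B, 3C".
- Cohort 3A: 175 / 3 = 58.3.
- Share of Cohort 3: 58.3 / 175 = 33.3%.
- Planned total: 120 + 50 + 175 + 130 = 475, so 58.3 / 475 = 12.3%.

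This is a maximum. The recruitment span is not given, so no lower count can be derived.

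**Step 4. What triggers it.**
- Above 50%, arm as cohort: 0.5 × 58.3 = 29.2, so 30 failures (30 / 58.3 = 51.4%; 29 / 58.3 = 49.7%).
- Above 50%, Cohort 3 as cohort: 0.5 × 175 = 87.5, so 88 failures.
- Early rule: 10 of the first 20.

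**Step 5. Timing.**
- 3B and 3C start BIW at week 28 + 4 = 32.
- 3A and 3B exit at week 56 (for 3B, 28 + 4 + 24). 3C starts QW at week 56 and exits at 56 + 28 = 84.
- Failed completers are known only from the Exit DBPCFC. Before week 56, the 50% count for subjects enrolled at about the same time rests on AE dropouts alone.
- A 3A subject enrolled on the same day as a 3B subject has 56 − 32 = 24 weeks of QD left when 3B starts BIW. A stop caused by QW dosing in 3C can reach only 3A subjects enrolled later.

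**Step 6. Size of the change for one subject.** QD is 7 doses a week and BIW is 2. Over those 24 weeks QD gives 24 × 7 = 168 doses. With 4 weeks of QOD (14 doses) and then 20 weeks of BIW (40 doses), the total is 54.

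**The case against.** The strongest reply is that nobody would apply the sentence this way. In the Synopsis it is the second half of a statement whose first half ends prolongation, so it reads naturally as a fallback for subjects on, or heading for, a longer interval. Protocol 3.1.5 sends cohort data to the SMC for review and a recommendation, and 7.8.3 has the SMC monitor the failure rate. The scenario is also narrow, no formal comparison depends on 3A, and about 58 is only a ceiling. All of this stands and is why the severity is low. It does not make the wording right: a safety rule should give the correct instruction without the reader having to supply the intent.

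It is also fair that the phrase about what a previous cohort tolerated is not defined. A cap does not cure that, but it makes a wrong judgment on it harmless for subjects on QD.

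Some stronger readings are tempting but not supported:
- A reader might infer that the switch would be abrupt. Protocol 6.3.8.1 does name only some cohorts: "Subjects in Cohorts 2, 3B, and 3C will change to BIW dosing once they have tolerated QOD dosing for 4 weeks". But the Figure 1 note is general: "The BIW interval begins with 4 weeks of QOD dosing before transitioning to 24 weeks of BIW dosing, as tolerated". Protocol 3.1.5 also requires the first two BIW doses to be supervised throughout extended maintenance.
- A reader might infer that Group 1 is exposed too. Protocol 3 and 3.1.5 deal specifically with Group 1, requiring sequential lengthening and SMC agreement before its daily regimen changes.
- A reader might infer that the rule fails when Cohort 1 stops, since no cohort precedes it. Cohort 1 is already on QD, so nothing changes in practice.

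**Conclusion.** The point holds as a low-severity wording error in a safety rule. As written, the sentence is an assignment, and in one plausible sequence it lengthens dosing for subjects assigned to QD. The size is at most about 58 planned subjects, about 12% of the planned 475.

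This rests on three conditions together: Cohort 2 tolerates BIW, a Cohort 3 arm then meets a stopping condition, and the sentence is applied literally without the guard or the SMC intervening.

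A reader might go further and infer that 3A subjects were in fact moved. The documents do not support that. SAP 2.3 records SMC advice that Cohort 3C subjects on BIW stay on BIW and Group 1 subjects on QD stay on QD, and SAP 6.1 summarizes Cohort 3A as QD only. The SAP does not report that a cohort stopping rule was met. This suggests that intervals were handled as a cap would require, but it does not correct the protocol text.

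**What to change.** Reword the sentence in Protocol 7.8.3 and its counterpart in the Synopsis as a ceiling:

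> No remaining or future subject will be dosed at an interval longer than the longest interval tolerated by a previous cohort (QD if there is none). No subject's interval will be lengthened because of a cohort stop. Subjects assigned to QD throughout (Cohorts 1 and 3A) remain on QD. Group 1 lengthens only under the SMC process in Section 3.1.5.

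The ceiling does not by itself stop 3B or 3C subjects in their 28-week QD lead-in from taking the scheduled step to BIW when BIW is within the cap. That stays with the SMC.

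The cost is a change to two sentences, with no added visits, procedures or staff. As a protocol amendment it needs sponsor, IRB/EC and health authority approval before use (Protocol 11.1) and a check of whether the consent form needs revision (Protocol 11.2).

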8 OPTIONAL MECHANISTIC STUDIES

Subjects from selected centers in ARC004 are eligible to participate in the optional collections of saliva and peripheral blood specimens to be collected for future studies designed to better understand the biological basis and treatment of food allergy. These additional specimens are entirely voluntary, do not affect the subject's participation in ARC004, and require separate informed consent. The additional tubes of peripheral blood are to be collected at the same time points as the routine laboratory work in ARC004 and do not require additional visits or phlebotomy. The saliva specimens will be collected as part of an ongoing collaboration with researchers at Cincinnati Children's Hospital Medical Center to analyze the salivary mRNA transcriptome of participants receiving OIT, as outlined further in [Appendix 6](#).

9 STATISTICAL CONSIDERATIONS

This protocol outlines the major statistical considerations for the ARC004 study. Full details on the statistical methodology to be used in the analysis and data handling for this trial will be described in the statistical analysis plan (SAP) to be developed prior to database lock and statistical analysis.

Data will be summarized using descriptive statistics within treatment group and cohort. No specific hypothesis testing or comparisons between the treatment groups is planned for this study. Details of within group and within cohort comparisons relative to baseline values and exploratory comparisons between cohorts will be described in the SAP.

Descriptive statistics will be presented in the following manner:

- Continuous data (ie, age, body weight, and height) will be summarized descriptively by mean, standard deviation, median, and range.
- Categorical data (ie, sex and race) will be presented as enumerations and percentages.

Data will be summarized by treatment group, cohort, and treatment phase (as defined in [Section 3.1](#)).

Data will be summarized in tables for each treatment group, treatment groups combined, and treatment phase (as defined in [Section 3.1](#)).

Data from ARC003 will be combined with ARC004 and will be used to define baseline, as appropriate. Additional details about combining data and handling varying exposure times will be described in the SAP. Data will be listed for each subject.

9.1 Analysis Populations

The primary population of analysis for all analyses will be the Safety population. The Safety population will consist of all subjects who receive study treatment during ARC004.

A Per Protocol (PP) population, limited to subjects who have no major protocol deviations and who undergo Exit DBPCFC, may be defined. Exclusions will be determined by data review and documented before database lock.

Additional analysis populations may be defined in the SAP.

9.2 Study Endpoints

9.2.1 Primary Endpoint

The primary endpoint is the frequency of treatment-related AEs, including SAEs, during the overall study period (from enrollment to the end of EM).

9.2.2 Secondary Endpoints

- Frequency of anaphylaxis
- Frequency of use of epinephrine as a rescue medication
- Frequency of AEs leading to withdrawal of AR101
- Frequency of AEs in each treatment regimen leading to discontinuation of extended interval dosing
- Frequency of GI AEIs
- Frequency of accidental food allergen exposure
- In subjects with asthma, change in asthma control using the Asthma Control Test questionnaire (see [Appendix 2](#))
- Frequency of all above safety endpoints by treatment period
- The proportion of subjects in each regimen tolerating ≥ 1043 mg cumulative of peanut protein during their EM Exit DBPCFC
- The proportion of subjects in each regimen who tolerate ≥ 443 mg cumulative of peanut protein during their EM Exit DBPCFC
- The proportion of subjects in each regimen who tolerate 4043 mg cumulative of peanut protein during their EM Exit DBPCFC

- Maximum tolerated dose and change from baseline* at Post-Maintenance** and each EM Exit DBPCFC
- Maximum severity of symptoms at each challenge dose at Post-Maintenance** and each EM Exit DBPCFC
- Frequency of use of epinephrine as a rescue medication at the Post-Maintenance** and each EM Exit DBPCFC
- Change in QoL as assessed by the FAQLQ and the FAIM questionnaire
- Satisfaction with AR101 treatment as assessed by the TSMQ-9 questionnaire and additional questions
- Changes in peanut-specific serum IgE and IgG4 levels
- Changes in peanut skin prick test (SPT) wheal diameter

*Baseline is defined as the Screening DBPCFC from ARC003 for both treatment groups.

**Post-Maintenance is defined as the ARC003 Exit DBPCFCs for Group 2.

